3 STUDY DESIGN

3.1 Main study design

This study is a prospective, randomized open-label clinical trial that will be conducted during the 2017-2018 influenza season. Results from the 2017-2018 influenza season will help guide whether this study will be repeated during the 2018-2019 influenza season under a new protocol. During the 2017-2018 season, approximately 280 children will be enrolled at Duke University Medical Center and Kaiser Permanente Northern California. Eligible children will be randomized to receive simultaneous or sequentially administered US-licensed PCV13, US-licensed DTaP vaccine, and US-licensed inactivated influenza vaccine (IIV). Children in the simultaneous group will receive PCV13, DTaP, and IIV vaccines at Visit 1, and then return for a health education visit without vaccination about 2 weeks later (Visit 2). Children in the sequential group will receive both PCV13 and DTaP without IIV at Visit 1, and then will receive IIV and health education about 2 weeks later (Visit 2). Parents will record the occurrence of fever, solicited adverse events, medical care utilization, and receipt of antipyretics over 8 days following Visit 1 and Visit 2. In addition, febrile seizures and serious adverse events will be recorded for the entire study period (from enrollment through 8 days following the Visit 2) will be assessed through parental report and chart review.

Young children aged 12-16 months will be enrolled over a period of approximately 7 months. Children will be followed for up to 37 days following enrollment. The first 10 children enrolled at Duke University Medical Center will be enrolled in a study pilot to quickly assess study feasibility benchmarks and make protocol adjustments if necessary. Data from pilot participants will also contribute to the analysis of primary, secondary and exploratory outcomes.

4 STUDY ENROLLMENT AND WITHDRAWAL

Subject Inclusion and Exclusion Criteria will be reviewed at Visit 1 to assess eligibility for study participation.

4.1 Subject Inclusion Criteria

Subjects who meet all of the following criteria will be eligible to participate in this interventional study.

1. 12 through 16 months of age (i.e. from the 1-year birthday until the day before 17 months of age) at the time of vaccination
2. Stable health as determined by investigator's clinical examination and assessment of child's medical history
3. Has received all immunizations recommended by Advisory Committee for Immunization Practices (ACIP) during the first year of life with the exception of rotavirus and influenza vaccines.*

**Immunizations recommended during the first year of life include: 3 doses of DTaP, 3 doses of PCV13, 2- 3 doses of inactivated polio virus vaccine, 3 doses of Hepatitis B vaccine, and 2 or 3 doses of Hib vaccine such that the primary Hib series is complete depending upon the brand used.*

(<https://www.cdc.gov/vaccines/schedules/hcp/imz/child-adolescent.html>).

4. The parent(s)/ legally authorized representative(s) LAR(s) intend for the child to receive DTaP and PCV13 in addition to this season's IIV
5. The parent(s)/LAR(s) must be willing and capable of providing permission for their child to participate through the written informed consent process
6. The parent(s)/LAR(s) must be able to comply with the requirements of the protocol (e.g., completion of the memory aid (either electronic or paper diary), return for follow-up visits, respects intervals between the visits and have telephone access.
7. The parent(s)/LAR(s) must be English speaking
8. The parent(s)/LAR(s) must agree to sign a medical release for the child so that study personnel may obtain medical information about the child's health (if needed)

4.2 Subject Exclusion Criteria

Subjects who meet any of the following criteria will not be eligible to participate in this study:

1. History of any seizure (including febrile seizure) in the child or a febrile seizure in a first degree relative*
**First degree relatives include biological parents or siblings*
2. Has already completed influenza vaccination during the current season per ACIP recommendations*
**Children needing two doses of influenza vaccine per ACIP recommendations and who are receiving a second dose of influenza vaccine may be enrolled; however, an attempt will be made to preferentially enroll children needing two doses at the time of receipt of their first dose of influenza vaccine*
3. Receipt of more than 3 previous doses of DTaP
4. Received the 3rd dose of DTaP within 6 months of Visit 1
5. Receipt of more than 3 previous doses of PCV13
6. Received the 3rd dose of PCV13 within 8 weeks of Visit 1
7. History of a severe allergic reaction (e.g. anaphylaxis) to a previous dose of any influenza, diphtheria toxoid-, tetanus toxoid-, or pertussis-containing vaccine, or pneumococcal vaccine.
8. History of a severe allergic reaction (e.g., anaphylaxis) to any component (including egg protein) of any of the three vaccines used in this study; or a latex allergy.

9. History of Guillain-Barré syndrome within 6 weeks following a prior dose of influenza, DTaP, or tetanus toxoid containing vaccine
10. History of a progressive neurologic disorder
11. History of encephalopathy within 7 days of a previous pertussis-containing vaccine
12. History of collapse within 3 days after a prior dose of DTaP
13. Received any other licensed vaccines within 14 days (for inactivated vaccines) or 28 days (for live vaccines) prior to Visit 1*
**Concomitant vaccine administration of vaccines on ACIP recommended immunization schedule for children and adolescents aged 18 years and younger are allowed to be administered on the first vaccination day in this study but at no other time in this study period unless deemed a personal or public health priority by the health care provider caring for this patient or the study team.*
14. Received an experimental/investigational agent (vaccine, drug, biologic, device, blood product, or medication) within 28 days prior to Visit 1, or expects to receive an experimental/investigational agent during the study period (up to 8 days after visit 2)
15. A moderate to severe acute illness within 72 hours of Visit 1*
**All vaccines can be administered to persons with a minor illness such as diarrhea, mild upper respiratory infection without fever.*
16. A reported temperature greater than or equal to 100.4°F (38.0°C) within 72 hours prior enrollment or a temperature (measured by temporal artery thermometer) greater than or equal to 100.4°F (38.0°C) at the time of enrollment*
**This may result in a temporary delay of vaccination*
17. Receipt of an antipyretic medication (acetaminophen or ibuprofen) within 24 hours prior to enrollment*
**This may result in a temporary delay of vaccination*
18. Parent(s)/LAR is planning to administer a prophylactic antipyretic or medication on the day of, and/or within 7 days following Visit 1 or Visit 2*
**This exclusion does not apply if the caretaker indicates he/she might administer antipyretics or analgesics after vaccination to reduce fever or pain*
19. Long term (at least 14 consecutive days) oral corticosteroids (prednisone 2 mg/kg/day or equivalent other glucocorticoid), any parenteral steroids, high-dose inhaled steroids (>800 mcg/day of beclomethasone dipropionate or equivalent) or other immune-modifying drugs or immunosuppressants within the preceding 6 months prior to Visit 1*
**Topical and nasal steroids are allowed*
20. Any confirmed or suspected immunosuppressive or immunodeficient condition, based on medical history and or their provider's routine physical examination*
**No laboratory testing required*
21. Has an active neoplastic disease, a history of any hematologic malignancy, current bleeding disorder, or taking anticoagulants.
22. Unable to receive an intramuscular injection in the thigh*
** For example – a broken bone or cast for treatment of broken bone in a lower extremity, congenital anomaly in lower extremity precluding administration in the affected extremity or if deemed inappropriate by the study investigator*

23. Any condition deemed by the investigator to place the child at increased risk as a result of their participation in the study
24. Any child or grandchild of a study investigator or study team member

A modified list of Exclusion Criteria will be reviewed at Visit 2 to assess eligibility for continued study participation.

Subjects who meet any of the following exclusion criteria will not be eligible to continue participation in this study:

1. Has already completed influenza vaccination during the current season per ACIP recommendations
2. History of a severe allergic reaction (e.g. anaphylaxis) to a previous dose of any influenza vaccine.
3. History of a severe allergic reaction (e.g., anaphylaxis) to any component (including egg protein) of the influenza vaccine used in this study.
4. History of Guillain-Barré syndrome within 6 weeks following a prior dose of any influenza vaccine
5. Received an experimental/investigational agent (vaccine, drug, biologic, device, blood product, or medication) after randomization or expects to receive an experimental/investigational agent during the remaining study period (up to 8 days after visit 2)
6. A moderate to severe acute illness within 24 hours of Visit 2*
** This may result in a temporary delay of Visit 2 and/or vaccination.
All vaccines can be administered to persons with a minor illness such as diarrhea, mild upper respiratory infection without fever.*
7. A reported temperature greater than or equal to 100.4°F (38.0°C) within 24 hours prior to Visit 2 or a temperature (measured by temporal artery thermometer) greater than or equal to 100.4°F (38.0°C) at the time of Visit 2*
**This may result in a temporary delay of Visit 2 and/or vaccination*
8. Receipt of an antipyretic medication (acetaminophen or ibuprofen) within 24 hours prior to Visit 2*
**This may result in a temporary delay of Visit 2 and/or vaccination*
9. Parent(s)/LAR is planning to administer a prophylactic antipyretic or medication on the day of, and/or within 7 days following Visit 2*
**This exclusion does not apply if the caretaker indicates he/she might administer antipyretics or analgesics after Visit 2 to reduce fever or pain*
10. Unable to receive an intramuscular injection in the thigh*
** For example – a broken bone or cast for treatment of broken bone in a lower extremity, congenital anomaly in lower extremity precluding administration in the affected extremity or if deemed inappropriate by the study investigator*
11. Any condition deemed by the investigator to place the child at increased risk as a result of their participation in the study

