 - Parent(s)/LAR(s) electing to use REDCap will only be called/contacted on Study Day 3 following Visit 1 if missing fever information or if out of range fever values and will only be called/contacted on Study Day 9 following Visit 1 if missing information
 - All parent(s)/LAR(s) electing to use the paper memory aid only will be called/contacted on Study Day 3 following Visit 1.
 - All children will return for a visit on Visit 2 on Day 15. Remind parents using paper memory aid only to return memory aid at Visit 2.

Visit 1A, Study Day 3 (window Days 3-6) Memory Aid Check - Phone Call/E-mail Follow-up

- *REDCap Follow-Up for Memory Aid Information*
 - Review of REDCap information submitted for fever only on Day 1 and Day 2 for completeness and out of range values for fever.
 - If missing fever information or out of range fever values, contact parent(s)/LAR(s) to review the memory aid data for Day 1 and Day 2 and obtain any missing fever information or clarify any out of range fever values.
 - Instruct parent to enter any missing days of data in REDCap

- Record missing information regarding fever on paper case report form (CRF)
- If missing days of information for solicited adverse events, medical care utilization, antipyretic use, occurrence of febrile seizure or occurrence of a serious event remind parent to complete information in REDCap,
- *Paper Memory Aid Completion*
 - Contact parent(s)/LAR(s) to review and obtain Day 1 and Day 2 memory aid information for fever only (completeness and out of range values)
 - Record information regarding fever on paper CRF
 - Remind parent(s)/LAR(S) to bring the paper memory aid to Visit 2
 - Confirm date of next scheduled clinic visit appointments.

Visit 1B, Study Day 9 (window Days 9-12) Memory Aid Check – Phone Call/E-mail Follow-up

- *REDCap Follow-Up for Memory Aid Information*
 - Review of electronically submitted memory aid information (fever, solicited adverse events, medical care utilization, antipyretic use, occurrence of febrile seizure, or occurrence of a serious adverse event) for Days 1-8 for completeness
 - If missing information, contact parent(s)/LAR(s) to review the memory aid data for Days 1-8 and obtain any missing information
 - Instruct parent to enter missing days of data into REDCap
 - Record missing information on a paper CRF
- *Paper Memory Aid Completion*
 - No scheduled follow-up for this visit

Visit 2, Study Day 15 (window Days 15 – 22) Clinic Visit

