This document stands to serve as a general guideline for the study investigators to a priori define major protocol violations. Participants with major protocol violations will not be included in the Per Protocol Population.

Major Protocol Violations Defined:

1) Inclusion/Exclusion Criteria Violations

Did Not Meet Study Inclusion Criteria	At Study Entry Visit 1	During Period of Enrollment¹
1. 12 through 16 months of age (i.e. from the 1-year birthday until the day before 17 months of age) at the time of vaccination	X	X
2. Stable health as determined by investigator's clinical examination and assessment of child's medical history	X	
3. Has received all immunizations recommended by Advisory Committee for Immunization Practices (ACIP) during the first year of life with the exception of rotavirus and influenza vaccines.* *Immunizations recommended during the first year of life include: 3 doses of DTaP, 3 doses of PCV13, 2- 3 doses of inactivated polio virus vaccine, 3 doses of Hepatitis B vaccine, and 2 or 3 doses of Hib vaccine such that the primary Hib series is complete depending upon the brand used. (https://www.cdc.gov/vaccines/schedules/hcp/imz/child-adolescent.html).	X	X
4. The parent(s)/ legally authorized representative(s) LAR(s) intend for the child to receive DTaP and PCV13 in addition to this season's IIV	X	
5. The parent(s)/LAR(s) must be willing and capable of providing permission for their child to participate through the written informed consent process	X	
6. The parent(s)/LAR(s) must be able to comply with the requirements of the protocol (e.g., completion of the memory aid (either electronic or paper diary), return for follow-up visits, respects intervals between the visits and have telephone access.	X	
7. The parent(s)/LAR(s) must be English speaking	X	
8. The parent(s)/LAR(s) must agree to sign a medical release for the child so that study personnel may obtain medical information about the child's health (if needed)	X	
Met Exclusion Criteria		
1. History of any seizure (including febrile seizure) in the child or a febrile seizure in a first degree relative* *First degree relatives include biological parents or siblings	X	X
2. Has already completed influenza vaccination during the current season per ACIP recommendations* *Children needing two doses of influenza vaccine per ACIP recommendations and who are receiving a second dose of	X	X

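### The Visit 2 exclusion for completed influenza vaccination does not exempt the dose that the study itself gave as assigned

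*Combined protocol and SAP*

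**What the plan says.** Protocol 4.2 ends with a second list of exclusions: "A modified list of Exclusion Criteria will be reviewed at Visit 2 to assess eligibility for continued study participation". Its opening sentence is "Subjects who meet any of the following exclusion criteria will not be eligible to continue participation in this study", and item 1 is "Has already completed influenza vaccination during the current season per ACIP recommendations". The list is addressed to all subjects. Item 1 has no footnote, although items 6 to 10 have one; items 7 and 8, for example, carry "This may result in a temporary delay of Visit 2 and/or vaccination".

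The corresponding entry criterion (exclusion 2) does have a footnote. It says that children who need two doses and "who are receiving a second dose of influenza vaccine may be enrolled", and SAP Appendix 1 repeats that footnote ("Children needing two doses of influenza vaccine per ACIP recommendations and who are receiving a second dose of").

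SAP Appendix 1 lists Visit 2 item 1 in the same words, again unqualified, and marks it both at Visit 2 and in the column for the period after Visit 2. Appendix 1 states that children with major violations are left out of the Per Protocol population. Protocol 4.4 names meeting a Visit 2 exclusion as a possible reason for withdrawal.

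The design sections expect something else. Protocol 3.1 and SAP 4.1 have the simultaneous group vaccinated with all three products at Visit 1 and returning for an education-only Visit 2. Protocol 5.1 says "All children will return for a visit on Visit 2 on Day 15". Protocol 5.4 requires temperatures after Visit 2 in the simultaneous group too. SAP 9 calls for a comparison of first and second seasonal influenza doses in both the ITT and the Per Protocol populations.

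**The concern.** A child can meet item 1 simply by receiving what was assigned. In the simultaneous arm the study gives influenza vaccine at Visit 1. If that dose is the last one needed for the season, the child has completed vaccination by the time eligibility is reviewed at Visit 2. This covers children enrolled for a second dose, and any child who needs only one.

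If the item is followed as written, Per Protocol membership for fully adherent children depends on something the study did to them and, on the natural reading, on the arm they were allocated to. If it is set aside by judgement, that judgement is made in an open-label trial and the plan records no rule for it, although Appendix 1 exists to define major violations in advance.

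**Working it through.** **1. Follow one child through each arm.** Take a child whose study influenza dose completes the season.

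- *Simultaneous arm.* The dose is given at Visit 1 (protocol 3.1). At the Visit 2 review the season is complete, so item 1 is met. Literal result: not eligible to continue (4.2), and a major violation excluded from Per Protocol (Appendix 1).
- *Sequential arm, natural reading.* In the Visit 2 procedures of protocol 5.1 the eligibility review is listed before the influenza vaccine, so item 1 is not yet met. The Appendix 1 footnote to the later column concerns the study team learning after Visit 2 that an exclusion had been met, not events that follow. Literal result: not caught.
- *Sequential arm, alternative reading.* If the mark in the later column is taken to count the Visit 2 dose itself, this child has also completed the season. Literal result: caught in Per Protocol, so adherent children in both arms are lost.

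A child who needs two doses and receives the first at Visit 1 is not caught at Visit 2 in either arm.

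**2. Compare with the rest of the plan.** Neither result for the simultaneous child fits protocol 3.1, 5.1 and 5.4 or SAP 4.1. Under the one-arm reading, the Per Protocol second-dose comparison in SAP 9 would contain no simultaneous-arm children.

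**3. Reproduce the planned power.** Inputs from protocol 6.1 and SAP 4.2: fever 36% simultaneous and 18% sequential, 126 per group, two-sided 0.05. With the pooled-variance normal approximation, unstratified:

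- p̄ = (n₁p₁ + n₂p₂)/(n₁ + n₂)
- SE₀ = √[p̄(1 − p̄)(1/n₁ + 1/n₂)]
- SE₁ = √[p₁(1 − p₁)/n₁ + p₂(1 − p₂)/n₂]
- power = Φ[(|p₁ − p₂| − 1.96·SE₀)/SE₁]

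For 126 and 126: p̄ = 0.270, SE₀ = 0.0559, SE₁ = 0.0548, z = 1.285, power 90.1%. The plan's 90% is reproduced.

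**4. Illustrate the loss.** The share of simultaneous children affected is not in the documents. I assume 10%, 20% and 30% of 126 (12.6, 25.2 and 37.8, rounded to 13, 25 and 38), keep 126 sequential children, and leave both rates unchanged.

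| Assumed share | Simultaneous n | p̄ | SE₀ | SE₁ | z | Power |
|---|---|---|---|---|---|---|
| 10% | 113 | 0.265 | 0.0572 | 0.0567 | 1.199 | 88.5% |
| 20% | 101 | 0.260 | 0.0586 | 0.0588 | 1.109 | 86.6% |
| 30% | 88 | 0.254 | 0.0605 | 0.0616 | 0.999 | 84.1% |

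The relative risk stays at 0.36/0.18 = 2.0, because the rates were held fixed.

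**5. ITT.** Membership is set at Visit 1 (SAP 6.1), so no child leaves. But if a child were actually withdrawn at Visit 2, the Visit 2 window would be unobserved, and SAP 8.1 scores the absence of a reported fever as 0. A child already febrile after Visit 1 would still count; a first fever after Visit 2 would be missed. With withdrawals in the simultaneous arm only, this could only lower that arm's observed proportion.

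**The case against.** The best reply is that the intent is recoverable. Items 2 to 4 and 10 of the Visit 2 list bear on giving influenza vaccine, which at Visit 2 only the sequential arm receives, so item 1 reads naturally as part of the same check and as aimed at vaccine obtained outside the study. Appendix 1 treats receiving products contrary to assignment as a violation, so receiving them as assigned can hardly be meant as one. Withdrawal reasons are permissive (4.4), major violations are for the investigators to determine (SAP 6.2), and Appendix 1 calls itself a guideline. Protocol 4.2 prefers to enrol two-dose children at their first dose, which limits the number affected. The starting figure of 126 is already net of a 10% dropout allowance, into which some removals might fall. The entry footnote only permits enrolment; carried over unchanged, it would not clearly exempt a dose already given.

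All of this stands as a limit on the practical effect. None of it supplies the exemption: the rule as written still conflicts with the design sections, and discretion to ignore an express criterion should be written down.

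A reader might go further and infer that the item strikes the simultaneous arm alone. That depends on treating the later column in Appendix 1 as late discovery only. This is the more natural reading, but the text does not settle it. A reader might also infer that the Per Protocol relative risk would be inflated by a definite amount. Protocol 1.1 reports only that the co-administration effect was greater after the first dose in one earlier observational study. It gives no ratio, and no document gives the share of second-dose children, so such a figure would be invented.

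**Conclusion.** The point holds as a minor wording defect with a literal consequence that contradicts the design. I am confident that the exemption is missing and that a simultaneous-arm child whose assigned dose completes the season is caught as written. Whether sequential children are caught as well depends on how Appendix 1 is read.

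The practical effect is probably small and its size cannot be derived from the documents. The fall in Per Protocol power to between 88.5% and 84.1% is an illustration. It rests on an assumed 10% to 30% affected, removal of every such child, loss from the simultaneous arm only, and unchanged fever rates. Two inferences should be avoided: that children would be removed automatically, which the discretion in protocol 4.4 and SAP 6.2 contradicts; and that ITT is wholly untouched, which fails if a child is in fact withdrawn before the Visit 2 temperatures are recorded.

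**What to change.** Reconcile Visit 2 item 1 in protocol 4.2 and its copy in SAP Appendix 1 with protocol 3.1, 5.1 and 5.4 and SAP 4.1 and 9. In both places, state that influenza vaccine given by the study according to randomized assignment (at Visit 1 in the simultaneous arm, at Visit 2 in the sequential arm) does not count toward this item, either for continued follow-up or for Per Protocol membership. Naming both arms also closes the ambiguity in the column for the period after Visit 2. Leave the item otherwise unchanged; no change to who is vaccinated is proposed.

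The cost is one sentence in each document. No further data are needed, since receipt of a first influenza dose is already a baseline variable (SAP 7.1). Little is given up in Appendix 1: entry exclusion 2 still covers completion before Visit 1, and a separate entry still covers vaccines given during the study away from Visits 1 and 2.

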4.4 Reasons for and Handling of Withdrawals

The following may be reasons for study withdrawal:

- As deemed necessary by the principal investigator (PI).
- Meets criteria for exclusion at Visit 2
- Parent(s)/LAR(s) withdrawal of permission for their child to participate.
- Loss to follow-up.
- No longer a member of the Kaiser Foundation Health Plan (KFHP) – only includes children enrolled at the Northern California Kaiser Permanent pediatric clinics.
- Termination of the study by the sponsor.

A parent/LAR may withdraw permission for their child to participate at any time and for any reason, without penalty. Subjects who are withdrawn from the study prior to randomization or first vaccination visit will be replaced. Subjects who are withdrawn from the study after receiving vaccine will not be replaced. For subjects who received study vaccines, data collected prior to withdraw in the study will be included in the study.

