6.1 Sample Size and Power Estimation

Allowing for a 10% drop out rate given an initial N=280, there should be approximately 252 children enrolled into the study. If the true proportion of children who have fever on day 1 and/or day 2 after the first and/or second visit in the simultaneous group is 36%

and the true proportion in the sequential group is 18%, then there is 90% power to reject the null hypothesis of no difference with N=126 per group with a two-sided alpha 0.05 level. This is based upon using a Mantel-Haenszel statistic in a stratified analysis to control for sites.

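### The Visit 2 exclusion list ends follow-up of randomised, vaccinated children, so Visit 2 fever data can be lost in a way that depends on arm and on the Visit 1 result

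*Combined protocol and SAP*

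**What the plan says.** Protocol 4.2 gives a second exclusion list, applied at Visit 2 to children already randomised and vaccinated. Its lead-in is unconditional: "Subjects who meet any of the following exclusion criteria will not be eligible to continue participation in this study". Item 9 reads "Parent(s)/LAR is planning to administer a prophylactic antipyretic or medication on the day of, and/or within 7 days following Visit 2", with a note exempting caretakers who might give medicine to reduce fever or pain. Items 6 to 8 (acute illness, recent fever, recent antipyretic) carry a note allowing Visit 2 or vaccination to be delayed; item 9 does not. Protocol 4.4 includes "Meets criteria for exclusion at Visit 2" among the possible reasons for withdrawal. It also says that data collected before withdrawal are kept for children who received study vaccine. No section provides for temperature collection after such a withdrawal.

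Entry exclusion 18 already removes families planning prophylaxis after either visit. The trial is open label (5.5.2), and the footnote to Table 1 confines Visit 2 vaccination to the sequential group.

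On analysis, ITT requires randomisation and one study vaccine at Visit 1 (SAP 6.1). SAP 8.1 scores fever on day 1 or 2 after either visit as 1 and the absence of a reported fever as 0. Per Protocol drops children without valid day 1 and 2 temperatures after both visits (SAP 6.2). SAP Appendix 1 lists Visit 2 item 9, and also a missed Visit 2, as major violations: "Participants with major protocol violations will not be included in the Per Protocol Population". Both populations are analysed and neither is named primary.

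**The concern.** Because of entry criterion 18, item 9 can catch only plans formed after enrolment, in most cases by parents who know the allocation and have seen how the child reacted to Visit 1. A sequential-arm parent faces another vaccine at Visit 2; a simultaneous-arm parent faces a health-education visit. So the chance of meeting the criterion can differ by arm and can depend on Visit 1 fever.

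The rationale in Protocol 1.2 is to learn whether separating the vaccines reduces fever or only spreads it over two occasions. For a child afebrile after Visit 1, that question turns on the Visit 2 window, which is what the rule stops being measured. The secondary outcome SOM 1.2 (fever after Visit 2) loses that window for every withdrawn child, whatever happened after Visit 1. None of the sensitivity analyses in SAP 9 deals with a missing Visit 2 window.

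**Working it through.** **The plan's own figure.** Protocol 6.1 says: "Allowing for a 10% drop out rate given an initial N=280", about 252 remain (280 × 0.90 = 252), and with 36% v 18% "then there is 90% power to reject the null hypothesis of no difference with N=126 per group with a two-sided alpha 0.05 level". With the pooled-variance normal approximation:

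- null standard error = √(2 × 0.27 × 0.73 / 126) = 0.0559
- alternative standard error = √((0.36 × 0.64 + 0.18 × 0.82) / 126) = 0.0548
- z = (0.18 − 1.96 × 0.0559) / 0.0548 = 1.28, so power = 90.1%

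The stated power reproduces. The planned relative risk is 0.36 / 0.18 = 2.00.

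**Inputs for the illustrations.**

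- p1 is the sequential-arm fever rate after Visit 1. The documents do not give it. Protocol 1.1 reports 9.5% for PCV13 alone; I take 9.5% to 15%, below the planned 18% for both visits together.
- u is the share of sequential children whose only fever would follow Visit 2 and who are withdrawn before it is seen: 5% to 25%, assumed.
- w is the share of sequential children febrile after Visit 1 who are withdrawn: 10% to 50%, assumed.
- The simultaneous arm is held at 36% with no such loss, except in the direction check.

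**ITT, child febrile after Visit 1.** The endpoint is already positive and the data are kept. The sequential rate stays at 18.0% and the relative risk at 2.00 for every w.

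**ITT, child afebrile after Visit 1, then withdrawn.** Read literally, SAP 8.1 scores this child 0. Children whose only fever follows Visit 2 make up 0.18 − p1 of the arm, so the recorded rate is 0.18 − u(0.18 − p1).

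| p1 | u | Sequential rate | Relative risk | Fevers missed of 126 |
|---|---|---|---|---|
| 9.5% | 5% | 17.6% | 2.05 | 0.5 |
| 9.5% | 25% | 15.9% | 2.27 | 2.7 |
| 15% | 5% | 17.9% | 2.02 | 0.2 |
| 15% | 25% | 17.3% | 2.09 | 0.9 |

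As a check on plausibility, suppose withdrawal is unrelated to whether fever would have followed. Then at p1 = 9.5%, u = 25% means withdrawing 0.25 × 0.905 × 126 = 28.5 children, against a planned dropout of 14 per arm (280 × 0.10 / 2). At u = 5% it is 5.7 children. The upper end is a bound, not an expectation.

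**Per Protocol.** The child leaves numerator and denominator together, so the rate is (0.18 − w·p1) / (1 − w·p1). With p1 = 9.5%:

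- w = 10%: 0.1705 / 0.9905 = 17.2%; relative risk 2.09; 1.2 children of 126 lost
- w = 50%: 0.1325 / 0.9525 = 13.9%; relative risk 2.59; 6.0 children lost

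If the schedules truly did not differ (18% in both arms), the same losses would give a relative risk of 1.05 to 1.29.

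**Direction check.** The rule covers both arms. In the study cited in Protocol 1.1, fever was 37.6% after IIV with PCV13 and 9.5% after PCV13 alone, so more simultaneous-arm children may be febrile after Visit 1. Assume 33% there and a 10% withdrawal share in both arms. The simultaneous Per Protocol rate is (0.36 − 0.033) / (1 − 0.033) = 33.8%, the sequential rate is 17.2%, and the relative risk is 1.96, slightly below 2.00.

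**The case against.** The strongest reply has five parts.

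- **Few families are caught.** Entry criterion 18 has already removed those with such a plan, and a parent who only stands ready to treat a new fever is exempt. This stands: it makes large withdrawal shares less plausible, and no document gives a rate of changed plans.
- **ITT keeps the febrile children.** This stands in full for a child febrile after Visit 1. It does not cover a child afebrile after Visit 1, whose endpoint is still open when follow-up stops.
- **Per Protocol loss is not peculiar to item 9.** A child without valid Visit 2 temperatures, or with no Visit 2, is out anyway. That is true, but for a withdrawn child those data are missing because the protocol ends participation.
- **Item 9 has a purpose.** Prophylaxis could mask Visit 2 fever. That is fair, and it is a reason not to alter the criterion. It does not require follow-up to end.
- **Protocol 4.4 is permissive.** It lists possible reasons for withdrawal. The 4.2 lead-in, however, is absolute, and nothing describes follow-up of a child who meets a criterion but is not withdrawn.

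A reader might infer more: that the rule strips febrile sequential-arm children out of the primary comparison and so tilts the trial toward its hypothesis. The documents do not support that. In ITT those children remain fever cases, and in Per Protocol the direction depends on how the unknown losses fall between the arms.

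**Conclusion.** The point holds in a limited form. A post-randomisation rule ends outcome measurement in children already randomised and vaccinated, and in this open-label design the loss can depend on arm and on the Visit 1 result.

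The ITT exposure is confined to children afebrile after Visit 1 and is probably small: 0.2 to 2.7 missed fevers of 126 over the assumed range. It also rests on the literal scoring in SAP 8.1. Per Protocol is more exposed because recorded fevers are discarded as well. SOM 1.2 is exposed in either population.

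The withdrawal shares, the Visit 1 fever rates and the absence of loss in the simultaneous arm are all assumptions. With equal shares in both arms the Per Protocol effect can reverse, so no direction of bias is established. The point merits correction because the gap is created by the protocol, cannot be repaired in analysis, and is cheap to close.

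**What to change.** Leave the Visit 2 criteria for giving vaccine as they are, and separate them from follow-up.

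- In Protocol 4.2 and 4.4, state that meeting a Visit 2 criterion does not end participation. In place of withdrawal on that ground, continue the day 1 to 8 temperature and antipyretic diary from the actual or scheduled Visit 2 date, remotely if needed, unless the parent withdraws permission.
- In the SAP, name ITT, including these windows, as the primary analysis.
- Report Visit 2 exclusions by arm, reason and Visit 1 fever status.

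The cost is wording changes and a few more diaries; families already have the thermometer and the memory aid. The downside is that some Visit 2 windows will be without IIV or affected by antipyretics, which can lower recorded fever. The daily antipyretic record and the antipyretic sensitivity analysis already planned in SAP 9 allow the antipyretic part to be examined; reporting exclusions by arm shows how many windows are involved. No position is taken on antipyretic use or on who should be vaccinated at Visit 2.
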